7.2.17 Underdosed or overdosed patient (current NOAC treatment)

The recommended dose of dabigatran is 150mg twice a day (BID). Patients who meet any of the following criteria should perform a dose adjustment to 110mg BID, so those who receive the recommended dose of 150mg BID will be classified as overdosed. Those who receive a 110mg BID dose and do not meet any of the following criteria will be classified as underdosed:

- Age ≥ 80 years
- Patients aged 75-79 years and HAS-BLED ≥ 3
- Moderate renal impairment (creatinine clearance 30-50mL/min)

The recommended dose of rivaroxaban is 20mg once a day (QD). Patients who meet the following criteria should perform a dose adjustment to 15mg QD, so those who receive the recommended dose of 20mg QD will be classified as overdosed. Those who receive a 15mg QD dose and do not meet following criteria will be classified as underdosed:

- Moderate renal impairment (creatinine clearance 30-50mL/min) or severe renal impairment (creatinine clearance 15-29mL/min)

The recommended dose of apixaban is 5mg BID. Patients who meet at least 2 of the following 3 criteria should perform a dose adjustment to 2.5mg BID, so those who receive the

Document:	H:\HOR-Europe\2019\2512352 - Study on anticoagulation management - BI\Proyecto\Estadistica\SAP\S		
	AP_REBELD_version1.0_08072020.docx		
Author:		Version Number:	Version 1.0
		Version Date:	[08072020]

Template No.: RWI_TP_BIOS0013 Revision 1

Reference: RWI_WI_BIOS0015

Effective Date: 15Jun2018

recommended dose of 5mg BID will be classified as overdosed. Those who receive a 2.5mg BID dose and do not meet at least 2 of the 3 following criteria will be classified as underdosed:

- Age \geq 80 years
- Body weight \leq 60 kg
- Serum creatinine \geq 1,5 mg/dl or severe renal impairment (creatinine clearance 15-29mL/min)

The recommended dose of edoxaban is 60mg OD. Patients who meet at least 1 of the following 2 criteria should perform a dose adjustment to 30mg OD, so those who receive the recommended dose of 60mg OD will be classified as overdosed. Those who receive a 30mg OD dose and do not meet at least 1 of the 2 following criteria will be classified as underdosed:

- Body weight \leq 60 kg
- Moderate or severe renal impairment (creatinine clearance 15-50mL/min)

A categorical variable for dose category with 3 levels will be described:

- 1) Appropriately dosed
- 2) Underdosed
- 3) Overdosed.

7.3 Software Version

All analyses will be conducted using SAS Enterprise Guide version 7.15.

Document:	H:\HOR-Europe\2019\2512352 - Study on anticoagulation management - BI\Proyecto\Estadistica\SAP\SAP_REBELD_version1.0_08072020.docx		
Author:		Version Number:	Version 1.0
		Version Date:	[08072020]

Template No.: RWI_TP_BIOS0013 Revision 1

Reference: RWI_WI_BIOS0015

Effective Date: 15Jun2018

8. STATISTICAL CONSIDERATIONS

Continuous variables will be described by the number of patients with valid/missing observations, mean, SD, median, 25 and 75 percentiles (Q1 and Q3, respectively), minimum and maximum and categorical variables will be described by frequencies and related percentages. Appendix 1 on page 42 shows the summary TLFs to be provided in the report of the study.

8.1 Statistical Bias Reduction

No statistical methods for handling bias will be used. Given the real-world nature of the data and the descriptive purposes of the study objectives no confounding factor have been identified.

Missing values and drop-outs will be counted in all description of variables, but no imputation will be considered.

8.2 Statistical Tests and Confidence Intervals

No statistical test will be performed.

8.3 Adjustments for Covariates and Factors to be Included in Analyses

No statistical modelling will be done. So, no adjustment for covariates and factors to be accounted for in the analyses are considered.

8.4 Missing data

Given the real-world nature of the data and the descriptive purposes of most of the study objectives, study variables will not be imputed. Missing values and drop-outs will be counted

Document:	H:\HOR-Europe\2019\2512352 - Study on anticoagulation management - BI\Proyecto\Estadística\SAP\S		
	AP_REBELD_version1.0_08072020.docx		
Author:		Version Number:	Version 1.0
		Version Date:	[08072020]

Template No.: RWI_TP_BIOS0013 Revision 1

Reference: RWI_WI_BIOS0015

Effective Date: 15Jun2018

in all description of variables, but no imputation will be considered. Only date data where the exact day is missing will be imputed, being replaced by the middle of the month.

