7. GENERAL CONSIDERATIONS

The design of the study imposes a single visit to be performed and that will coincide with one of those performed by the patients as part of routine follow-up of their disease, without interfering with usual clinical practice of the investigator.

Data will be collected through an eCRF which will include all the study variables.

Investigator will enter patient data in eCRF. Variables collected at the time of the study visit (including those related to the first NOAC initiation) will be obtained based on and limited to those available in the medical records of the selected patients. Demographic characteristics, smoking habit and alcohol consumption may be asked to the patient at the study visit if not available in the medical records. LVEF measurement will be obtained from the last images available for the patient.

Document:	H:\HOR-Europe\2019\2512352 - Study on anticoagulation management - BI\Proyecto\Estadistica\SAP\SAP_REBELD_version1.0_08072020.docx		
Author:		Version Number:	Version 1.0
		Version Date:	[08072020]

Template No.: RWI_TP_BIOS0013 Revision 1

Reference: RWI_WI_BIOS0015

Effective Date: 15Jun2018

Clinical Frailty Scale, modified EHRA scale for AF related symptoms, NYHA classification for heart failure, CHA2DS2-VASc and HAS-BLED scores will be assessed by the investigators at the study visit by evaluating the patient's functional status and medical records and the values will be directly included in the eCRF.

Final score for the Comorbidities Charlson Index will be automatically calculated based on the answers individually entered by the investigator in the eCRF for each index item (6).

Any required missing data to calculate the score for the scales or the Comorbidities Charlson Index may be asked to the patient at the study visit if not available in the medical records and should be documented, however the final score number obtained by the investigator from this information will not need to be included in medical records.

Boehringer Ingelheim reserves the right to discontinue the study overall or at a particular study site at any time for the following reasons:

1. Failure to meet expected enrolment goals overall or at a particular study site
2. Administrative reasons (i.e. study rejected by the hospital director)
3. Violation of GxP (as applicable), the study protocol, or the contract by a study site or investigator, disturbing the appropriate conduct of the study

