Comorbidities and Clinical Risk Factors: - Heart Failure (Yes/No, New York Heart Association (NYHA) classification; Left Ventricular Ejection Fraction, LVEF, %) - Coronary artery disease (Yes/No) - Sleep apnoea-hypopnoea syndrome (SAHS) (Yes/No) - Hypertension (Yes/No) -Hyperlipidemia (Yes/No) - Comorbidity Charlson index (Yes/No; total score): myocardial infarction (already collected for history of thromboembolic events), congestive heart failure (already collected for the NYHA scale scoring), cerebral and peripheral vascular disease, dementia, chronic obstructive pulmonary disease, connective tissue disease, peptic ulcer disease, mild/moderate/severe liver disease, diabetes, diabetes with end-organ damage, hemiplegia, moderate/severe renal disease, any solid tumor, metastatic solid tumor, leukemia, lymphoma AIDs, age (already collected as a demographic characteristic). -History of thromboembolic events (Yes/No, number and date): TIA, ischemic stroke, hemorrhagic stroke, embolism systemic, deep vein thrombosis, pulmonary embolism, stable angina, unstable angina, myocardial infarction with/without ST segment elevation; and bleeding events (Yes/No, number and date): intracranial, digestive, genitourinary, gingival, nasal, pulmonary, articular-muscular, conjunctival.	x	x (NYHA classification, Charlson Index)
CHA2DS2-VASc (total score)		x
HAS-BLED (total score)		x
Clinical Frailty Scale		x
Previous vitamin K antagonist (VKA) treatment (yes/no), type (acenocoumarol or warfarin), start date and treatment duration		
Other concomitant treatments (Total number of current concomitant drugs; Type (Yes/No, number): ARB or ACE inhibitor, Beta-blocker, Calcium channel blockers, Diuretics, Amiodarone, Statin, Proton pump inhibitor, H2-receptor antagonist, Digoxin, NSAIDs, Dronedarone, Other antiarrhythmics, ketoconazole (systemic), cyclosporine, itraconazole	x	

Document: H:\HOR-Europe\2019\2512352 - Study on anticoagulation management - BI\Proyecto\Estadística\SAP\S AP_REBELD_version1.0_08072020.docx

Author: [REDACTED] Version Number: Version 1.0
Version Date: [08072020]

Template No.: RWI_TP_BIOS0013 Revision 1

Reference: RWI_WI_BIOS0015

Effective Date: 15Jun2018

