14.6 Exploratory analysis

History and current antiplatelet treatment will be described by current NOAC type.

Treatment received at the time of thromboembolic and bleeding events will be described, including NOAC, VKA and antiplatelet treatments.

Doses of current NOAC treatment received by the patient will be described according to HAS-BLED score (as low, intermediate and high risk).

The percentage of underdosed and overdosed patients for current NOAC treatment will be described.

HAS-BLED total score (as <3 , $3-5$, ≥ 5) will be described according to NOAC and antiplatelet current treatment.

Multivariate logistic regression will be used to evaluate the association between the Clinical Frailty Scale (dependent variable: Frailty patients - CFS scoring >4 vs Non-frailty patients - CFS scoring ≤ 4) and the thromboembolic and the bleeding events (independent variables). To calculate this analysis, only events that have occurred subsequent to the start of anticoagulant therapy (not those prior to the start of VKA / NOACs) will be considered. Other factors will be age, sex, BMI, smoking habit, alcohol consumption, time since NVAf diagnosis, NVAf type, modified EHRA scale, procedures and interventions, comorbidity Charlson index and clinical risk factors. Univariate analysis will be performed. All variables which have a P value of less than 0.1 will be included in the multivariate analysis.

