17.4 Additional tables

Table 45. Historic and current antiplatelet treatment according to current NOAC type

		Dabigatran	Rivaroxaban	Apixaban	Edoxaban	Total
Antiplatelet treatments received (all)	Valid N Aspirin Clopidogrel Prasugrel Ticlopidine Ticagrelor Cilostazol Triflusal Dipyridamole					

Document: H:\HOR-Europe\2019\2512352 - Study on anticoagulation management - BI\Proyecto\Estadistica\SAP\SAP_REBELD_version1.0_08072020.docx

Author: [REDACTED] Version Number: Version 1.0
Version Date: [08072020]

Template No.: RWI_TP_BIOS0013 Revision 1

Reference: RWI_WI_BIOS0015

Effective Date: 15Jun2018

		Dabigatran	Rivaroxaban	Apixaban	Edoxaban	Total
	Others N missing					
Time in treatment with antiplatelet agents (in years)	Valid N Mean (SD) Median (Q1-Q3) Min-Max N missing					
Current antiplatelet treatment (at study visit)	Valid N None Aspirin Clopidogrel Prasugrel Ticlopidine Ticagrelor Cilostazol Triflusal Dipyridamole Others N missing					

Table 46. Treatment received at the moment of thromboembolic events (1st part)

		TIA	Ischemic stroke	Hemorrhagic stroke	Embolism systemic	Deep vein thrombosis
Treatment (VKA/NOAC/antiplatelet)	Valid N* No Yes N missing					
VKA	Valid N* No Yes N missing					
Type of VKA	Valid N Acenocoumarol Warfarin N missing					

Document: H:\HOR-Europe\2019\2512352 - Study on anticoagulation management - BI\Proyecto\Estadistica\SAP\S AP_REBELD_version1.0_08072020.docx

Author: [REDACTED] Version Number: Version 1.0
Version Date: [08072020]

Template No.: RWI_TP_BIOS0013 Revision 1

Reference: RWI_WI_BIOS0015

Effective Date: 15Jun2018

		TIA	Ischemic stroke	Hemorrhagic stroke	Embolism systemic	Deep vein thrombosis
NOAC	Valid N* No Yes N missing					
Type of NOAC	Valid N Dabigatran Rivaroxaban Apixaban Edoxaban N missing					
Antiplatelet	Valid N* No Yes N missing					
Type of antiplatelet	Valid N Aspirin Clopidogrel Prasugrel Ticlopidine Ticagrelor Cilostazol Triflusal Dipyridamole Others N missing					

*Number of events in each column.

One event could be associated with more than one treatment

Document: H:\HOR-Europe\2019\2512352 - Study on anticoagulation management - BI\Proyecto\Estadística\SAP\S
AP_REBELD_version1.0_08072020.docx

Author: [REDACTED] Version Number: Version 1.0
Version Date: [08072020]

Template No.: RWI_TP_BIOS0013 Revision 1

Reference: RWI_WI_BIOS0015

Effective Date: 15Jun2018

Table 47. Treatment received at the moment of thromboembolic events (2nd part)

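### Mid-month imputation does not preserve date order, so when an event and an anticoagulant start share a calendar month and one day is missing, the exploratory frailty model can misclassify the event as before or after treatment.

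*SAP*

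**What the plan says.** SAP 8.4 (Missing data) leaves study variables unimputed, with one exception: "Only date data where the exact day is missing will be imputed, being replaced by the middle of the month". The rule covers every date. It has no exception for event or treatment dates, no order check and no rule for ties.

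Two analyses in SAP 14.6 depend on timing:

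- **Frailty model (Table 53).** "only events that have occurred subsequent to the start of anticoagulant therapy (not those prior to the start of VKA / NOACs) will be considered". SAP 4.6 repeats this restriction.
- **Treatment at the event (Tables 46-49).** "Treatment received at the time of thromboembolic and bleeding events will be described, including NOAC, VKA and antiplatelet treatments". Tables 46-47 cover thromboembolic events and Tables 48-49 bleeding sites. The SAP does not say how treatment at the event is obtained.

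SAP 4.6 lists both analyses as additions to the protocol. In Protocol Table 3, thromboembolic events are recorded as yes/no with a number and bleeding events as yes/no, neither with a date. SAP Table 3 adds dates: "History of thromboembolic events (Yes/No, number and date", and likewise for bleeding. For VKA it lists "type (acenocoumarol or warfarin), start date and treatment duration". It does not state the precision of these dates and lists no variable for treatment at the event.

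According to SAP 7, the data "will be obtained based on and limited to those available in the medical records of the selected patients".

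**The concern.** The model needs the order of two dates. The imputation rule keeps each date close to its true value but does not keep their order. That is harmless when the dates are months apart, but not when both fall in one calendar month.

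Such pairs can occur when an event leads to anticoagulation within days, or when a bleed follows soon after a start. An event before treatment could then enter a model whose stated rule excludes it, and an event on treatment could be dropped. If Tables 46-49 are built from dates, the drug shown against an event could also be wrong. Those tables split events by type and then by drug, so cells may be small and a few misplaced events could be visible.

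**Working it through.** The plan gives no figure on this point, so there is nothing to reproduce. The check applies the SAP 8.4 rule and then the SAP 14.6 test of event after start.

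**Inputs**

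- From the documents: a missing day becomes mid-month, taken here as the 15th; an event counts only if it follows the start.
- Assumptions: a 30-day month, the interval between event and start, and the share of dates without a day. The documents give neither the interval nor the share.

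**Example.** The true event is on 3 June with the day missing, and the NOAC starts on 10 June. The imputed event is 15 June, after the start, and would be day 6 of NOAC treatment.

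**Event on or before the start, same month.** There are 30 × 31 / 2 = 465 equally likely day pairs.

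- Only the event day missing: the event moves after the start when the start is on day 14 or earlier. 14 × 15 / 2 = 105; 105/465 = 22.6%.
- Only the start day missing: this happens when the event is on day 16 or later. 15 × 16 / 2 = 120; 120/465 = 25.8%.
- Both missing: both become the 15th and tie. Read strictly, a tied event is not subsequent to the start. The duration formulas in SAP 7.2 add 1 and so count the start date as treated, which would place a tied event on treatment.

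**Event after the start, same month (reverse error).** There are 30 × 29 / 2 = 435 pairs.

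- Only the event day missing: the event moves to on or before the start when the start is on day 15 or later. 120/435 = 27.6%.
- Only the start day missing: this happens when the event is on day 15 or earlier. 105/435 = 24.1%.

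**Without the same-month condition.** The event day is uniform over 30 days, the lag from event to start is uniform, and month-crossing pairs are kept:

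| Lag (assumed) | Only event day missing | Only start day missing |
|---|---|---|
| 0-7 days | 84/240 = 35.0% | 92/240 = 38.3% |
| 0-14 days | 105/450 = 23.3% | 120/450 = 26.7% |

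**Fixed lags on calendar dates.** For all event dates in 2014-2018 with only the event day missing, the share moved after the start is 42.7% at 1 day, 23.0% at 7 days, 13.1% at 10 days and 0% from 14 days. The average is 21.4% for a uniform lag of 1-14 days, 10.0% for 1-30 and 3.3% for 1-90. With only the start day missing it is 27.7% at 7 days and 0% at 20 days. In the reverse direction, with the event day missing, 31.0% of events 7 days after the start move to on or before it.

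**Number of patients.** This can only be illustrated. Assume 500 patients, 10-30% with a prior event, 25-100% of event days missing, and 25-100% of starts within 14 days of the event:

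- Low end: 500 × 0.10 × 0.25 × 0.25 × 0.214 = 0.7.
- High end: 500 × 0.30 × 1 × 1 × 0.214 = 32.1.

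The range of about 1 to 32 reflects the assumed inputs, covers one direction only, and is not an estimate.

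**The case against.** The strongest reply is that nothing shows the relevant dates lack days. The only date specified without a day is the NVAF diagnosis, collected as month and year. Protocol 9.6 plans eCRF checks that flag missing or illogical entries, so some gaps may be resolved before SAP 8.4 applies. Mid-month imputation is a common convention, and the analyses are exploratory. All of this stands: the frequency is unknown and could be near zero. It does not remove the gap, because SAP 8.4 expects partial dates, the source is retrospective records, and no rule protects the order.

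A reader might infer more: that the rule systematically turns events that triggered treatment into events on treatment, inflating counts under NOAC or VKA and biasing the Table 53 odds ratios one way. The documents do not support that, for four reasons.

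- The one-way argument holds only for triggering events. Early post-start events, including bleeds, move the other way.
- Secondary prevention, as a reason for the first NOAC, says nothing about the interval between event and start. Same-month timing is possible but not shown to be usual.
- For a patient already on VKA, an event before the first NOAC may already qualify for the model. An error at the NOAC start would then change only the drug attributed.
- Tables 46-49 have no stated derivation. The SAP follows CRF version 2, which is not among the documents, so direct recording of treatment at the event cannot be excluded.

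**Conclusion.** The gap is real and narrow. As written, SAP 8.4 can reverse the order on which SAP 14.6 relies, and nothing else in the plan prevents it. Among same-month pairs with the event on or before the start, 22.6% flip if only the event day is missing and 25.8% if only the start day is missing; if both are missing, the order is lost. These shares assume a 30-day month, imputation to the 15th and equally likely day pairs. With only the event day missing, the flip disappears once the lag reaches about 14 days.

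Neither the net direction of bias nor the number of events affected can be established. The frailty model is exposed by its own selection rule; Tables 46-49 are exposed only if they are derived from dates. The primary outcome, current NOAC type and dose, does not depend on these dates.

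**What to change.** Add to SAP 8.4 and 14.6:

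1. Do not use an imputed day to order an event against any anticoagulant start, stop or switch in the same calendar month.
2. Use the recorded order where the medical records or eCRF give it.
3. Otherwise class the order as indeterminate and report how many events this affects.
4. Run the Table 53 model twice, with these events counted as before the start and then as after it.
5. State how treatment at the event is obtained for Tables 46-49. If it is derived from dates, show these events in an indeterminate row or tabulate them both ways.

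Keep mid-month imputation elsewhere. Classing all such events as pre-start would be simpler, but it would move early on-treatment bleeds to before treatment. Covering stops and switches matters because a rule limited to the first start would leave events around a change of drug open to misattribution.

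The cost is a few SAP lines and one extra model run, with a second set of Tables 46-49 if they are tabulated both ways, and a small indeterminate group to report.

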7.2.7 Duration since the first NOAC

The number of months since the first NOAC initiation date until the study visit date will be obtained as follows:

Duration since the first NOAC (months) = (date of study visit – date of first NOAC + 1)/(30.5).

Duration since the first NOAC initiation until study visit will be categorized as >4 months and ≤4 months.

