7.2.8 Duration since NVAF diagnosis until first NOAC initiation

The number of months since the NVAF diagnosis date until the first NOAC initiation date will be obtained as follows:

Duration since the NVAF diagnosis until first NOAC initiation (months) = (date of first NOAC – date of NVAF diagnosis + 1)/(30.5).

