11. DEMOGRAPHIC AND OTHER BASELINE CHARACTERISTICS

Demographic data and other baseline characteristics will be presented for the FAS.

The following demographic and other baseline characteristics, related to secondary outcome, will be collected from medical records or at study visit to describe the patient's characteristics:

Table 3. Patient characteristics at the time of study visit

Variable	Obtained from medical records	Obtained at the study visit
Demographic characteristics: Age, sex, height, weight, BMI, caregiver (Yes/No), place where patient is living (Home alone; At home with	x	x

Document: H:\HOR-Europe\2019\2512352 - Study on anticoagulation management - BI\Proyecto\Estadistica\SAP\SAP_REBELD_version1.0_08072020.docx

Author: [REDACTED] Version Number: Version 1.0
Version Date: [08072020]

Template No.: RWI_TP_BIOS0013 Revision 1

Reference: RWI_WI_BIOS0015

Effective Date: 15Jun2018

Variable	Obtained from medical records	Obtained at the study visit
partner/other family member/a friend; Other's home (e.g family member's); Nursing home)		
Smoking habit (past/current/non-smoker) and alcohol consumption (casual or non-consumer/habitual/abuse/dependence)	x	x
Analytical lab results (from last available blood sample analysis): - Kidney function: serum creatinine (mg/dl), creatinine clearance (Cockcroft-Gault calculation) - Liver function: AST/ALT (UI/L), total bilirubin (mg/dl) - Haemoglobin (g/dl) and platelet levels (x uL)	x	
NVAF: - Diagnosis date (month and year) - Type (persistent, long standing persistent, permanent, paroxysmal) - Modified EHRA scale for AF related symptoms	x	x (mEHRA scale)
Procedures and interventions: - Cardioversion/Ablation (Yes/No) - Coronary interventions (Yes/No): Percutaneous coronary intervention (PCI)/Coronary Artery Bypass Grafting (CABG) - Pacemaker carrier (Yes/No)	x	

Document: H:\HOR-Europe\2019\2512352 - Study on anticoagulation management - BI\Proyecto\Estadistica\SAP\S AP_REBELD_version1.0_08072020.docx

Author: [REDACTED] Version Number: Version 1.0
Version Date: [08072020]

Template No.: RWI_TP_BIOS0013 Revision 1

Reference: RWI_WI_BIOS0015

Effective Date: 15Jun2018

Variable	Obtained from medical records	Obtained at the study visit

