14.2.2 OAC treatment management

OAC treatment management (since first NOAC initiation until the study visit date), based on the following variables:

- Previous vitamin K antagonist (VKA) treatment (yes/no), VKA treatment duration in years
- Duration since NVAF diagnosis until first NOAC initiation,
- Duration of first NOAC treatment (first NOAC active substance, start and stop date, first NOAC dose and its dose changes),
- Switch to new NOAC (active substance, start/stop date, dose and dose changes, reason for switch to new NOAC): number of patients that switch their first or further NOAC and mean number of switches.
- Total time in NOAC treatment
- History and current antiplatelet treatment (yes/no, start date, end date, active substance).

Patients will be also stratified by the duration since the first NOAC initiation date until the study visit date (> 4 months / ≤ 4 months).

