14.3.2 OAC treatment management

For OAC treatment management, descriptive analysis of previous VKA treatment (yes/no), VKA treatment duration in years, first NOAC treatment duration, first NOAC dose and dose changes, new NOAC treatment duration, new NOAC dose and dose changes. Duration since NVAF diagnosis until first NOAC initiation and total time in NOAC treatment will be described. Also, the reason for switches, the number of patients that switched their first or further NOAC and mean number of switches will be presented. Antiplatelet use will be also summarized.

Document:	H:\HOR-Europe\2019\2512352 - Study on anticoagulation management - BI\Proyecto\Estadistica\SAP\SAP_REBELD_version1.0_08072020.docx		
Author:	██████████	Version Number:	Version 1.0
		Version Date:	[08072020]

Template No.: RWI_TP_BIOS0013 Revision 1

Reference: RWI_WI_BIOS0015

Effective Date: 15Jun2018

The subgroup analysis of these outcomes by the duration since the first NOAC initiation until the study visit date (> 4 months / ≤ 4 months) will also be performed. For this subgroup analysis, a minimum of 50 patients is required for each group.

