17.3.2 Secondary outcome: OAC treatment management

Table 36. Previous VKA treatment and duration according to duration since the first NOAC initiation

		≤4 months	>4 months	Total
Previous VKA	Valid N No Yes N missing			
Type of VKA	Valid N Acenocoumarol Warfarin N missing			
Years with Acenocoumarol	Valid N Mean (SD) Median (Q1-Q3) Min-Max N missing			
Years with Warfarin	Valid N Mean (SD) Median (Q1-Q3) Min-Max N missing			
Total VKA treatment duration in years	Valid N Mean (SD) Median (Q1-Q3) Min-Max N missing			

Table 37. Durations since NVAF diagnosis until first NOAC initiation, first NOAC received, first NOAC dose, dose changes and first NOAC treatment duration according to duration since the first NOAC initiation

		≤4 months	>4 months	Total
Months since NVAF diagnosis until first NOAC initiation	Valid N Mean (SD) Median (Q1-Q3)			

Document: H:\HOR-Europe\2019\2512352 - Study on anticoagulation management - BI\Proyecto\Estadística\SAP\SAP_REBELD_version1.0_08072020.docx

Author: [REDACTED] Version Number: Version 1.0
Version Date: [08072020]

Template No.: RWI_TP_BIOS0013 Revision 1

Reference: RWI_WI_BIOS0015

Effective Date: 15Jun2018

		≤4 months	>4 months	Total
	Min-Max N missing			
First NOAC received	Valid N Dabigatran Rivaroxaban Apixaban Edoxaban N missing			
First NOAC dose: Dabigatran	Valid N 110mg BID 150mg BID N missing			
First NOAC dose: Rivaroxaban	Valid N 15mg QD 20mg QD N missing			
First NOAC dose: Apixaban	Valid N 2.5mg BID 5mg BID N missing			
First NOAC dose: Edoxaban	Valid N 30mg QD 60mg QD N missing			
Changes in first NOAC dose	Valid N No Yes (increase) Yes (decrease) N missing			
First NOAC treatment duration in years*	Valid N Mean (SD) Median (Q1-Q3) Min-Max N missing			
Reason for first NOAC treatment discontinuation*	Valid N Lack of effectiveness Investigator decision			

Document: H:\HOR-Europe\2019\2512352 - Study on anticoagulation management - BI\Proyecto\Estadistica\SAP\S
AP_REBELD_version1.0_08072020.docx

Author: Version Number: Version 1.0
Version Date: [08072020]

Template No.: RWI_TP_BIOS0013 Revision 1

Reference: RWI_WI_BIOS0015

Effective Date: 15Jun2018

		≤4 months	>4 months	Total
	Patient decision Adverse event N missing			
Reason for first NOAC treatment change dose*	Valid N Lack of effectiveness Investigator decision Patient decision Adverse event N missing			

BDI: twice a day; QD: once a day

*Only patients who stopped first NOAC treatment

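### Setting a month-and-year NVAF diagnosis date to mid-month gives negative diagnosis-to-NOAC times for some patients who started in the diagnosis month

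*SAP*

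**What the plan says.** Three rules act together.

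- **Collection.** SAP section 11, Table 3 lists "Diagnosis date (month and year"), and Protocol Table 3 does the same. The day is therefore absent by design, not by accident.
- **Imputation.** SAP 8.4: "Only date data where the exact day is missing will be imputed, being replaced by the middle of the month". The SAP does not say whether this is day 15 or day 16, and it does not limit the imputed date by any later known date.
- **Derivation.** SAP 7.2.8 takes the first NOAC date minus the diagnosis date, adds one day and divides by 30.5. It gives no floor and no rule for a negative result.

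The first NOAC is recorded in more detail. SAP 14.2.2 lists "first NOAC active substance, start and stop date, first NOAC dose and its dose changes", with no restriction to month and year.

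The derived time is part of the second secondary outcome. SAP 14.3.2 states: "Duration since NVAF diagnosis until first NOAC initiation and total time in NOAC treatment will be described". Mock Table 37 reports "Months since NVAF diagnosis until first NOAC initiation" with mean, SD, median, quartiles and range, in columns by time since first NOAC.

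**The concern.** A patient diagnosed and started on a NOAC early in the same month has the diagnosis moved forward to mid-month, past the real NOAC start. The formula then returns a negative time from diagnosis to treatment, which cannot occur if diagnosis came first. The patients affected are those treated promptly.

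The eCRF edit checks in Protocol 9.6 would not catch this. They act on entered data, and here the conflict arises only when the day is imputed at analysis.

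At stake is whether Table 37 prints an impossible minimum and a misplaced lower tail. Without a rule, the programmer would also have to decide after seeing the data whether to keep, zero or delete such values. A negative value produced by the rule could not be told apart from one that reflects a real date error.

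**Working it through.** The documents state no figure for this point, so there is none to reproduce.

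**Inputs.** Let G be the true diagnosis day, S the NOAC start day in the same month, and m the imputed day (15 or 16; the SAP does not specify). S is assumed to be known to the day.

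**Which start days go negative.** SAP 7.2.8 gives D = (S - m + 1)/30.5.

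| m | Negative | Zero | Minimum (S = 1) |
|---|---|---|---|
| 15 | days 1-13 | day 14 | (1 - 15 + 1)/30.5 = -0.43 months |
| 16 | days 1-14 | day 15 | (1 - 16 + 1)/30.5 = -0.46 months |

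A start in any later month gives a positive value, so only same-month starters are affected.

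**Share negative among same-month starters (30-day month, m = 15).**

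- NOAC started on the day of diagnosis, days uniform: 13/30 = 43.3%.
- All ordered pairs G ≤ S equally likely: there are 30 × 31/2 = 465 pairs. Those with S ≤ 13 number 1 + 2 + … + 13 = 91, and 91/465 = 19.6%.
- Over months of 28 to 31 days and m = 15 or 16, the range runs from 91/496 = 18% to 14/28 = 50%.
- A simulation with exponential delays (30-day month, m = 15) gives 38% at a mean delay of 3 days and 21% at 90 days.

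**Number of patients.** The documents give no share of same-month starters. If it were 10% to 30% of the planned 500 (an assumption), the count would run from 50 × 0.196 ≈ 10 to 150 × 0.433 ≈ 65. In the simulation with a 90-day mean delay, 15.4% start in the diagnosis month and 20.8% of those are negative: 0.154 × 0.208 ≈ 3% of all patients.

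**Effect on the mean.** For each patient the error is (G - m)/30.5, whatever the delay. With G uniform on 1-30 the mean of G is 15.5. The cohort mean therefore shifts by (15.5 - 15)/30.5 = +0.016 months for m = 15, or -0.016 for m = 16: half a day either way.

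**Effect on the lower quartile.** Q1 itself becomes negative only if more than 25% of the cohort is negative. At 43.3% this needs 0.25/0.433 = 58% of patients to start in the diagnosis month; at 19.6% it cannot happen. The minimum needs only one such patient.

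**If the NOAC day is also missing.** Both dates become the same mid-month day and D = 1/30.5 = +0.03 months, which is not negative.

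**The case against.** The best reply is that this is small. No value falls more than about half a month below zero, the variable is one component of a descriptive secondary outcome, SAP 8.2 plans no tests, and a negative minimum in Table 37 would be noticed. Patients who come from a VKA will rarely start a NOAC in the month of diagnosis. All of that stands and limits the weight of the point. It does not make the values valid, and noticing them at output stage is too late to choose a neutral rule.

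A reader might infer three stronger claims that the documents do not support.

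- **Many patients in the cohort are affected.** The 20% to 43% applies to same-month starters only, and their number is nowhere stated.
- **The mean is pulled down.** Forward shifts for early-month diagnoses are offset by backward shifts for late-month ones. For same-day starters with m = 15 the derived mean is 1.5/30.5 = 0.049 months against a true 1/30.5 = 0.033, so it is higher. The mean does fall among same-month starters under the ordered-pairs assumption (0.21 against 0.35), but Table 37 does not report that subset.
- **The same rule blurs the 4-month strata of SAP 7.2.7 or the 3-month entry criterion.** This would need first NOAC dates without a day. That date is not restricted to month and year, and nothing shows how often its day will be missing. Nor does any section say that eligibility is re-derived from imputed dates.

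**Conclusion.** The point holds in a limited form. Followed as written, SAP 8.4 and 7.2.8 produce impossible negative diagnosis-to-NOAC times for patients with a known NOAC start before about day 14 of the diagnosis month. With day 15, these are about 20% to 43% of same-month starters in a 30-day month, and the lowest value is -0.43 months. The harm is an invalid minimum and a distorted lower tail in Table 37, with no material shift in the cohort mean.

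This assumes that the NOAC start date carries a day, that diagnosis precedes or coincides with the start, and that diagnosis days are roughly uniform within the month. The absolute number of patients remains unknown. The primary outcome does not use this variable. Time from diagnosis to the study visit (SAP 7.2.5) cannot turn negative this way, because the NOAC must have begun at least 3 months before the visit.

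**What to change.** In SAP 7.2.8, replace the day-based formula with the difference in whole calendar months: 12 × (NOAC year - diagnosis year) + (NOAC month - diagnosis month), so that a start in the diagnosis month counts as 0. This uses only the precision collected and needs no imputed day. It cannot go negative when diagnosis precedes the NOAC, so any remaining negative value signals a real date conflict to query. The cost is one line in the SAP and one in the program, plus coarser values: a diagnosis at the end of one month with a start early in the next counts as 1.

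Two other remedies are not advised.

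- **Capping the imputed diagnosis date at the NOAC start.** This removes the negative errors but keeps the positive ones. For same-day starters with m = 15 the mean becomes 5/30.5 = 0.164 months against a true 0.033. In the simulation the cohort error rises from +0.016 to 0.016 + 0.915 × (0.176 - 0.085) = +0.10 months at a 3-day mean delay, and to 0.016 + 0.379 × (0.229 - 0.182) = +0.03 at 30 days.
- **Forcing imputed NOAC dates to satisfy the 3-month criterion.** This would assume eligibility and could hide violations that SAP section 10 plans to report.
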